8.10 Procedures for reporting any deviation(s) from the original statistical analysis plan

Any deviation(s) from the original statistical analysis plan will be reported in the final statistical analysis plan and in the clinical investigation report.

9. Data Management

Subject data will be entered into an electronic case report form (eCRF).

9.1 Source documents

The source documents (e.g., medical file, clinical and office charts, study worksheets, log for compliance data...) which contain the source of data being recorded in the eCRF should be specified. The paper diary will be used as source document for ARSSQ, concomitant treatments and adverse events/incidents reported by parents/legal guardians.

Each subject will be assigned and identified by a unique screening number. Any reference made to an individual subject within the study must be done using the unique screening number.

9.2 Methods for data entry and collection

A validated electronic case report form (eCRF, 21 CFR Part 11 compliant) will be used to collect clinical data for this study. Some of the study data will be recorded in the paper diary by parents/legal guardians:

- Daily ARSSQ
- Adverse events/incidents
- Concomitant treatments

Investigators will validate adverse events pertinent in the context of the common cold, incidents linked to medical device use and concomitant medications reported in the paper diary. They will complete the e-CRF accordingly.

The sponsor is responsible for designing the e-CRF. eCRF training will be provided to appropriate personnel before/at initiation of the investigation site. Parents/legal guardians will be instructed how to complete the paper diary during visit V1.

9.3 Procedure used for eCRF tracking, data review, database cleaning and issuing/resolving data queries.

The Data Management process includes all activities related to data handling regarding:

- Set-up of eCRF and database
- Specification of on-line checks
- Data entry/Data editing
- Export of data from e-CRF to SAS database
- Creation of post-entry checks and listings
- Clean-file process including execution of post-entry checks and listings
- Post clean-file tasks

Data entry will be done by investigators and other authorized personnel at the sites. When entering data, on-line checks are encoded in the eCRF for consistency and validation. Whenever required, queries issued from this review will be submitted to the investigator for resolution and then tracked until corrections are entered and validated.

A data blind review meeting will be held prior to database lock.

The data review meeting prepared by the project manager, data manager, study monitor, medical manager and statistician will be attended by at least the following:

- Coordinating investigator,
- Study monitor,
- Sponsor Vigilance representative,
- Project managers from the sponsor and from the CRO,
- Data manager,
- Statistician.

The review is also required for defining the analysis populations and validating the statistical analysis plan.

The meeting will be documented by written and signed minutes that will act as the basis for data processing by the Biometrics Department.

All decisions on the evaluability of the data from each individual subject for the statistical analysis must be made and documented before locking the database.

Data will be retained for at least 10 years after investigation closure. All data collected in the electronic Case Report Forms will be handled and archived under the responsibility of Lallemand Pharma.

9.4 Procedures for verification, validation and securing of electronic clinical data system

The EXAGIS software is installed on a Linux server (secure Data Center) hosted at the OVH company that guarantees the security, maintenance, as well as regular antivirus and firewall updates of this dedicated server. Any modification to the data is tracked, i.e. creation and changes are timestamped and authors are recorded. Software access is restricted to authorized users using individual encrypted passwords. Data processing via SAS software (SAS Institute, Cary, NC, USA) is carried out on a Windows 2012 R2 production server at OVH, using direct access by SAS or MySQL Workbench.

9.5 Procedures to maintain and protect subject privacy

It is the responsibility of the sponsor to maintain a security system that prevents unauthorized access to the data, both internally and externally.

Subject privacy is protected through the EXAGIS system at different levels to preclude unauthorized access to data:

• Only authorized persons can access the data:

Access to the database is restricted to authorized users using individual encrypted passwords. For all co-workers (from remote or on-site), an identification via a VPN is mandatory. Then, access to each server is always done through an authentication with a login and a personal password.

• The risk of data breaches:

The risk is minimized by full encryption and controlled access.

• External/internal interactions are actively protected:

A standard operating procedure (SOP) details all processes implemented for ensuring network security. This SOP mentioned the following subjects: system update, antivirus, antimalware, VPN management, user access accounts, password policy, training and awareness of coworkers, and data transfer security with partners/clients.

9.6 Methods for database locking at the start of analysis and storage upon completion of the clinical investigation

The validated database will be locked upon request of the Data Manager following the completion of all steps required, i.e. resolution of all queries, validation of the coding, data review meeting.

9.7 Procedure for data retention

Once the Clinical Investigation Report is signed and validated, the data are archived on a dedicated hard disk file with limited access rights. This specific file is mounted on AXIODIS's OVH server with a back-up every two months as well as copied to an external disk that will be stored under seal within the premises of AXIODIS. The data are conserved for at least 10 years.

Page 44 of 64

Version 1.1 –2023.02.02

Study Number: LPH-2202

10. Amendments to the CIP

Investigators should not implement any changes of the protocol without agreement by the sponsor.

All changes to the protocol are subject to an amendment which must be dated and signed by the sponsor and Principal Investigators and must appear as an amendment to the protocol.

Substantial amendments are notified to the EC and CA.

11. Deviation from Clinical Investigation Plan

A major protocol violation is a deviation that has an impact on subject safety, may substantially alter risks to subjects, may have an effect on the integrity of the study data, or may affect the subject's willingness to participate in the study. In this PMCF study, the following deviations are considered major:

- Non-compliance with the inclusion or exclusion criteria,
- No assessment of the primary efficacy criterion (ARSSQ) at D1, D5±1 and D8-1 during the treatment period,
- Intake of wrong treatment, i.e, wrong treatment given to the patient after randomization
- A compliance to study product intake below 80% or greater than 120%
- Intake of forbidden medication, i.e., nasal irrigation

All other cases will, a priori, be considered as minor deviations.

All protocol deviations will be managed as per the Standard Operating Procedures of the CRO.

A deviation log shall be maintained by the study site.

All deviations will be included, as required in the final study report.

Any major deviation from the protocol that has not been previously approved by the sponsor must be reported to the sponsor within 2 working days of the deviation occurrence. Any deviations from the clinical investigation plan that are identified during routine monitoring visits will be reported to the sponsor within 24 hours of being identified.

In case of major deviation, corrective and preventive actions will be implemented as per Study Deviation Management plan and Risk management plan.

12. Device accountability

The device accountability will be performed all over the study according to the SOP "Investigational Product Management" of the CRO. Briefly, sites will complete an accountability log after each receipt of the Medical Device and dispensation to parents/legal guardians. The CRA in charge of the site

monitoring will check the accountability log at each visit. At V2, the compliance will be assessed by weighing the device brought back by the parents/legal guardians.

Return of unused or expired investigational devices to the sponsor will be tracked using a specific record.

13. Ethical consideration

13.1 Informed Consent

According to Regulation EU 2017/745, ISO 14155:2020 and applicable Bulgarian regulations, the Principal Investigator or his/her authorized designee must explain all aspects of the clinical investigation that are relevant to the parents/legal guardians' decision for their child participation throughout the clinical investigation before any study procedure.

In order to ensure that the parents/legal guardians are fully informed the investigator must explain the nature of the clinical investigation, including any risks and benefits, its purpose and procedures, and expected duration of involvement in the clinical investigation. It must be made clear to the parents/legal guardians that participation of their child in the clinical investigation is voluntary and a decision not to participate will not affect their child right to the most appropriate treatment/care or affect the relationship with the doctor. Patients/legal guardians will have the opportunity to carefully review the information document and ask questions prior to accepting or not to participate in the study.

As this investigation is interventional, the consent shall be obtained in writing by both parents (except in specific situations as divorce with sole custody, widowhood) and the study participation must be documented in the patient medical file. But considering the specifics of the population, the children are not chronically ill, and that the screening/inclusion in the study can't be pre-planned, the written consent of only one parent at the screening visit is deemed acceptable with some conditions. Indeed, in case one parent would not be available for the visit, an oral consent (phone call) must be collected by the investigator during the visit and documented in the patient medical file. The second parent will be asked to sign the consent form at the earliest opportunity and to send it by e-mail to the investigator or to provide it on the next visit. The original of ICF with the signature of both parents shall be filed in the patient medical file.

In accordance with the "Ethical considerations for clinical trials on medicinal products conducted with minors" (Rev.1; 18 Sep 2017), no written assent will be collected for the children, because written assent is evaluated not to be obtainable before the school age (6-7 years). But, because children from the age of 3-4 years have some capacity of understanding, age- and maturity-appropriate information will be delivered by the investigator and the parents. Since textual information is not usable by most of these children, visual information using drawings will be used to ensure that the child is properly informed. The agreement of a child should be requested systematically, even if the assent is not legally required. Their refusal or dissent should be respected.

Parents/legal guardians reserve the right to withdraw from the clinical investigation at any time, irrespective of their initial consent. Objections raised by a child at any time during the trial should also

be considered. The child's will should be respected. The child should not be forced to provide reasons. The child should be informed of the possibility to freely withdraw from the trial, at any time for any reason, without any disadvantage or prejudice.

13.2 Subject confidentiality

The present study will be conducted under Regulation 2016/679/EU of the European Parliament and of the Council of 27 April 2016 on the protection of natural persons about the personal data and free movement of such data (GDPR) and PERSONAL DATA PROTECTION ACT, in force as from 1 January 2002.

In accordance with GDPR, the Sponsor is the "Controller" and the participating sites, monitors, data managers and statisticians are "Processors". Lallemand Pharma AG, sponsor of the study, is responsible for the processing of the study data.

Confidentiality of data shall be observed by all parties throughout the clinical investigation. All data will be secured against unauthorized access. Subject names will not be sent to the sponsor. Only the patient number will be recorded in the eCRF, and if the patient's name appears on any document, it must be obliterated before a copy of the document is supplied to the sponsor. All subject data that appear in reports and publications will be anonymised such that the privacy and confidentiality of each subject is maintained.

No data processing will be performed outside of the European Union.

To fulfil the requirements of source data verification, the PI will be required to obtain consent from each parent/legal guardian stating that they agree for their child's medical records to be accessed (this will form part of the consent process). To comply with GDPR, a specific document explaining the lawfulness of personal data processing conditions and patients' rights will be signed before any study procedure by the parents/guardians.

The patients' rights are the followings:

- The right to request access to, rectification, deletion or restriction of processing concerning personal data collected during the study,
- The right to get back all data linked to the research and to forward them to another data processing manager (portability right),
- The right to withdraw consent to data collection at any time and to request a restriction of
 processing concerning personal data as mentioned in GDPR's article 18. However, the data
 processing manager keeps the ability to reject such request should this right likely make
 impossible or seriously compromise the achievement of the research objectives.

These rights can be exercised with the investigator or his designated representative or by contacting the Data Protection Officer appointed by Lallemand Pharma: [name], [contact].

13.3 Insurance policy

Lallemand Pharma AG has an insurance policy intended to guarantee against possible damage resulting from the investigation.

It is advisable to underline that non-compliance with the Research Legal Conditions is a cause for guarantees exclusion.

14. Vigilance

14.1 General

Healsea® Babykids will be used in the intended use covered by the CE mark in this PMCF study.

Pursuant to (EU)2017/745 Medical Device Regulation, for a post market clinical follow-up investigation of a medical device used within the intended use covered by the CE-mark, requirement of MDR articles 87 to 90 apply (materiovigilance).

Nevertheless, if a causal relationship between a serious adverse event and an investigational procedure has been established, the safety reporting laid down in Article 80 of the MDR. Since the electronic system referred to in Article 73 (Eudamed) will not be available and fully functional at the date of study start, the procedures for safety reporting will be performed according to modalities described in the MDCG 2020-10/1 and -10/2.

All modalities of safety reporting will be detailed in a Safety Management Plan signed by the sponsor's vigilant, the Principal Investigators, the local CRA in charge of the monitoring and a representant of the CRO.

14.2 Definitions

Incident means any malfunction or deterioration in the characteristics or performance of a device made available on the market, including use-error due to ergonomic features, as well as any inadequacy in the information supplied by the manufacturer and any undesirable side-effect (MDR 2017/745).

Serious incident means any incident that directly or indirectly led, might have led or might lead to any of the following: (a) the death of a patient, user or other person, (b) the temporary or permanent serious deterioration of a patient's, user's or other person's state of health, (c) a serious public health threat (MDR 2017/745).

Serious public health threat means an event which could result in imminent risk of death, serious deterioration in a person's state of health, or serious illness, that may require prompt remedial action,

and that may cause significant morbidity or mortality in humans, or that is unusual or unexpected for the given place and time (MDR 2017/745).

Expected and foreseeable side effects (MEDDEV 2 12-1 rev. 8)

They meet all the following criteria:

- Clearly identified in the manufacturer's labelling,
- Clinically well known as being foreseeable and having a certain qualitative and quantitative predictability when the device is used and performs as intended,
- Documented in the device master record, with an appropriate risk assessment, prior to the occurrence of the incident and,
- Clinically acceptable in terms of the individual patient benefit.

Adverse event means any untoward medical occurrence, unintended disease or injury or any untoward clinical signs, including an abnormal laboratory finding, in subjects, users or other persons, in the context of a clinical investigation, whether related or not related to the investigational device (MDR 2017/745).

Adverse or intercurrent events are graded as follows:

- Mild: Awareness of signs or symptoms but easily tolerated.
- Moderate: Uncomfortable enough to cause interference with usual activity.
- Severe: Incapacity with inability to work or do usual activity.

Serious adverse event (SAE) (MDR Article 2(58)):

Any adverse event that led to any of the following:

- a) death,
- b) serious deterioration in the health of the subject, that resulted in any of the following:
 - i. life-threatening illness or injury,
 - ii. permanent impairment of a body structure or a body function,
 - iii. hospitalisation or prolongation of patient hospitalisation,
 - iv. medical or surgical intervention to prevent life-threatening illness or injury or permanent impairment to a body structure or a body function,
 - v. chronic disease,
- c) foetal distress, foetal death or a congenital physical or mental impairment or birth defect

14.3 Reporting in the eCRF

At V2, the investigator will validate the adverse events/incidents and concomitant medications reported in the paper diary by questioning the parent/legal guardian of the patient.

All serious and non-serious incidents/serious and non-serious risk of incidents/serious and non-serious adverse event (pertinent in the context of the common cold, additional study procedures and of the medical device use) occurring during the clinical investigation will be reported in the eCRF.

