6.3 Secondary Objectives

- To assess the impact of **Healsea® Babykids** on the duration of each infectious rhinitis symptom and on quality of life as compared to Placebo.
- To assess the impact of **Healsea® Babykids** on the intake of conventional common cold medication (antibiotics, antipyretics, mucolytics, decongestants, antitussives, systemic and topical corticosteroids) as compared to Placebo.
- Safety: to assess systemic and local tolerance of **Healsea® Babykids** over the study period.

6.4 Scientific justification and clinical relevance for effect sizes, noninferiority margins or equivalence

This is a PMCF study. The primary endpoint is a customized symptom and quality of life questionnaire. An arbitrary cohort of 200 children has been chosen. A cohort of 100 children in the Healsea® Babykids arm and 100 children in the Placebo arm is anticipated to allow to demonstrate the interest of using Healsea® Babykids in the acute infectious rhinitis. Indeed, 100 patients by arm are enough to detect a Cohen's effect size of 0.4 with a power of 80% and a type I error of 5%. Cohen's effect size is defined as the standardized difference between AUC in groups. According to Cohen's methodology, 0.4 is an intermediate size between a small effect (0.2) and a medium effect (0.5) and is coherent with the expected result. The Placebo arm will be used as the reference group.

The recruitment will be performed using a 1:1 randomization ratio.

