The investigator will provide the parents/legal guardians with the device according to the site specific treatment list, in order to respect the 1:1 randomization (blocks of 4). The investigator will explain how to use it.

NB: The first use of the device will be performed in the evening of the Day 1.

D1-D8 up to -D11 (at home):

The Parent/legal guardian will be asked to complete the ARSSQ in the diary, once daily in the evening. The symptoms occurring from the morning to the evening should be taken into consideration. The ARSSQ shall be scored at least from D1 to D8. Adverse events/incidents and concomitant medications are to be reported during the whole period

Between D8 and D11 (at home):

End of Healsea® Babykids/Placebo nasal spray.

➤ NB: The last study nasal spray intake will be performed **between D8 and D11** in the morning. The patient should stop taking the investigational device before D11 only if the question 1 "not sick" of the ARSSQ is ticked YES for 2 consecutive days.

Up to D15/D18 (at home):

Parents/legal guardians will continue to complete the paper diary daily (incidents/adverse events/expected undesirable sides effects, concomitant medications). For patients for whom common cold symptoms persist, parents/ legal guardians will be instructed to continue to complete the ARSSQ, until the subject feels not sick for two consecutive days.

Visit 2 (V2) - (Day 15-Day 18): end of study

The investigator or his/her delegated designee will:

- Perform a physical and clinical examination.
- Collect the patient diary.
- Review the paper diary to validate adverse events pertinent in the context of the common cold, incidents linked to medical device use and concomitant medications reported by the parents/legal guardians. Complete the e-CRF accordingly and report any new relevant safety events
- Ask parents/legal guardians to complete the ARSSQ if the patient still has symptoms.
- Assess the compliance to the treatment by weighing the device bottle returned by the parents/legal guardians. If a nasal spray is not returned or lost, the investigator will ask the

Version 1.1 –2023.02.02 Page **37** of **64**

Study Number: LPH-2202

parents/legal guardians to specify the number of missed nasal spray uses and will report the data into the e-CRF.

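### Adverse events, serious ones included, enter the eCRF only if judged pertinent, an undefined condition that leaves the SAP's outputs on non-related events incomplete

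*Protocol*

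**What the plan says.** **Entry rule.** Protocol 14.3 lists what goes into the eCRF: incidents and risks of incident, serious or not, and those adverse events, again serious or not, that are "pertinent in the context of the common cold, additional study procedures and of the medical device use". The Visit 2 instructions in 7.4.1 tell the investigator or a designee to "Review the paper diary to validate adverse events pertinent in the context of the common cold, incidents linked to medical device use", to fill in the eCRF on that basis, and to add newly found safety events if they are relevant. Section 9.2 repeats the rule: "Investigators will validate adverse events pertinent in the context of the common cold, incidents linked to medical device use", and then "They will complete the e-CRF accordingly".

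**Text without the condition.** Section 14.2 defines an adverse event as any untoward occurrence "in the context of a clinical investigation, whether related or not related to the investigational device". Section 7.1.4 says that events the parent writes in the diary are checked by the investigator at the final visit and then entered in the eCRF. The opening sentence of 14.3 also has the diary events checked with the parent, with no mention of pertinence.

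**Objective and endpoint.** The safety objective (Protocol 6.3, repeated in SAP 2.2) is "to assess systemic and local tolerance of" the device. The safety endpoint (Synopsis and 7.1.4) is narrower: adverse events related to acute rhinitis, plus incidents.

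**Analysis.** SAP 11.2 restricts the safety analysis to incidents, meaning events whose relationship to the device is anything other than not related. SAP 10.4 tabulates the non-related events, overall and treatment-emergent, by System Organ Class and Preferred Term. It also lists the serious non-related ones.

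**The concern.** The protocol uses a broad definition of an adverse event and collects events daily from parents. It then has the site decide, child by child, which of them count as pertinent before they become data. The term is not defined, and the condition is written to cover serious events too.

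The protocol expects no side effects from the device (5.2), so any new safety information would have to come from events nobody anticipated. An event that seems to have nothing to do with a cold or a nasal spray is the kind that a case-by-case judgement discards. Tabulating all events by arm is useful because it can show an imbalance that no single case would suggest, and it can show only what was entered. If the trial reports few or no non-related events, a reader cannot tell whether that reflects the children or the entry rule.

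**Working it through.** The plan states no figure on this point. The check is to follow each kind of event through the documents.

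1. **Device link suspected.** The incident definition in 14.2 includes undesirable side-effects. In 14.3 the pertinence condition most naturally attaches to adverse events, not to incidents. SAP 11.2 counts any relationship other than not related as an incident. These events are entered and analysed in full.

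2. **Not device-related, but pertinent.** Entered under 14.3 and tabulated under SAP 10.4. The three entry rules differ slightly: 14.3 names the cold, the study procedures and device use, whereas 7.4.1 and 9.2 name the cold and device-linked incidents only.

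3. **Not device-related, not pertinent, non-serious.** May appear in the diary, which is the source document (9.1). Not entered under 7.4.1, 9.2 or 14.3. Would be entered under 7.1.4. The passages disagree.

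4. **As 3, but serious.** Section 14.3 attaches the same condition. The separate route in 14.4.2 covers only serious events with a causal or reasonably possible link to an investigation procedure, and not-related events are excluded from reporting. The SAE form in Appendix D has the same limit. Section 14.4.2 does say that each serious event is classified on four causality levels, the first being not related. That presupposes such events are identified, but it does not say they go into the eCRF.

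So only kinds 3 and 4 are exposed. They fall wholly within the category that SAP 10.4 reports, and the SAP has no other source for them.

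**Illustration of lost sensitivity (assumed values, not in the documents).** Let *r* be the true risk per child of an unexpected systemic event of kind 3 or 4, and *c* the share of such events that pass the screen. With 100 children in the device arm (Protocol 6.4), the chance of at least one recorded case is

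P = 1 − (1 − *r* × *c*)^100.

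For *r* = 2% and *c* = 50%: 1 − (1 − 0.01)^100 = 63.4%.

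| Assumed risk | c = 100% | c = 75% | c = 50% | c = 25% |
|---|---|---|---|---|
| 1% | 63.4% | 52.9% | 39.4% | 22.1% |
| 2% | 86.7% | 77.9% | 63.4% | 39.4% |

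The table shows direction and shape only. Neither *r* nor *c* can be taken from the protocol or SAP.

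**The case against.** The strongest reply is that little is lost. Anything the investigator even possibly attributes to the spray is an incident and is not screened. This stands, and it confines the point to events judged both unrelated and not pertinent. A reader might infer that the whole tolerance assessment rests on screened data; the documents do not support that.

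Second, 7.1.4 and the first sentence of 14.3 carry no pertinence condition, and validating may mean no more than confirming an entry with the parent. A reader might therefore go too far in concluding that such events certainly never reach the database. What stands is that the sections conflict, and that the three giving the operative entry rule all contain the condition.

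Third, there are controls. Unreported events per site are tracked against thresholds (5.5.3), monitors compare the eCRF with source (7.5.2), and a Safety Management Plan (14.1), not among the documents, may say more. These help, but if the rule itself excludes an event, a monitor comparing diary and eCRF has no clear ground to query its absence.

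Fourth, this is a post-market study of a CE-marked class I device, and the endpoint may be narrow on purpose. That is a fair design choice. It would justify a narrower objective, but it does not reconcile the present objective with the present endpoint.

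Finally, a reader might infer bias between arms. Investigators are blinded (7.1.2), so the screen should act alike in both arms. No safety test is planned, and SAP 6.3.1 treats all results beyond the primary criterion as descriptive. That inference is not supported.

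**Conclusion.** The concern holds in limited form. Under Protocol 7.4.1, 9.2 and 14.3, an adverse event judged unrelated to the device and not pertinent need not be entered, even if serious. This conflicts with 14.2, with the eCRF reporting described in 7.1.4, and with an objective that includes systemic tolerance. It leaves the SAP 10.4 tables of non-related events and the listing of serious non-related events incomplete to an unknown degree.

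The likely effect is under-counting that does not differ by arm, with less chance of noticing an unexpected systemic event. The documents give neither the event rate nor the share screened out, so no size can be stated. The conclusion rests on two readings: that the condition in 14.3 applies to adverse events and not to incidents, and that completing the eCRF accordingly means entering only what passed the screen. The primary efficacy analysis is not affected.

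**What to change.** - In Protocol 7.4.1, 9.2 and 14.3, require every adverse event and serious adverse event noted in the diary or found at Visit 2 to be entered in the eCRF with seriousness, intensity and causality. The SAP's mock listing L3 already has columns for all three, so the change is mainly to the entry rule.
- Keep pertinence to the common cold as a yes/no flag on each event, so that the subset now planned can still be tabulated.
- Align the safety endpoint in the Synopsis and 7.1.4 with the objective in 6.3. Changing the entry rule alone would leave that mismatch in place.
- If the sponsor prefers the narrower collection, reword the objective and the safety conclusion to cover only what is collected, define the term, and state under the SAP 10.4 outputs that events judged not pertinent were not entered.

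The cost is a few more eCRF lines and some MedDRA coding per child, from a diary already kept for at most 18 days, plus revised protocol and eCRF wording. No extra visit or assessment is needed.
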